### 6.6.1 Definitions Related to Endpoints

**Absolute value (and/or percent) change from baseline:** Absolute value change and or percent change from baseline will only be summarized for patients with both baseline and post-baseline values for the relevant visit and will be calculated as:

Change from baseline = post-baseline value – baseline value

Percent change from baseline = (post-baseline value – baseline value)/baseline value\*100

**Treatment-emergent adverse events (TEAE):**

- Any AE that occurs after study treatment initiation.
- An AE that was present at the time of study treatment initiation but worsened after study treatment initiation.
- An AE that was present and resolved prior to treatment and reappeared after treatment initiation.
- Any treatment-related AE will always be considered treatment-emergent.

**NKTR-255 Treatment-emergent adverse events (TEAE) period:** Start of NKTR-255 through 30 days post last dose NKTR-255, or until a new antineoplastic regimen has been initiated, whichever comes first.

**Extended treatment-emergent adverse events (TEAE) period:** Start of any study drug through 60 days post last dose of study drug, or until a new antineoplastic regimen has been initiated, whichever comes first.

**Prior medications:** Prior medications are defined as medications with start date prior to C1D1.

**Concomitant medications:** Concomitant medications are defined as medications with stop date after C1D1, or medications with start date on or after C1D1 and up to 30 days after the last dose of NKTR-255. Medications with a start date after the initiation of any subsequent anticancer treatment will not be considered concomitant medications.

Medications with start date prior to C1D1 and end date after C1D1 will be classified as both prior and concomitant medications.

**Best overall response (BOR):** The BOR is defined as the confirmed best response designation over post-baseline response assessments. Disease assessments beyond progression or after start of subsequent therapy will not be considered for BOR.

**Overall response rate (ORR):** The ORR is defined as the proportion of subjects who have achieved PR or better as their BOR.

**Complete response rate (CRR):** The CRR is defined as the proportion of subjects who have achieved CR as their BOR.

**Responders:** Responders are defined as subjects with a confirmed BOR of PR or better. Ongoing responders are defined as responders who have not progressed, not died, not been off study and not started a subsequent therapy.

**Duration of response (DOR):** DOR is defined as the time from first response (PR or better) to the date of disease progression or death due to any cause, whichever occurs first. Subjects who remain alive and have not progressed are censored on the last evaluable disease assessment date (prior to subsequent cancer therapy). Same censoring rules for PFS apply to DOR. This endpoint is only defined for subjects with a confirmed BOR of PR or better.

**Time to response (TTR):** TTR is defined as the time from treatment start date (i.e. first dose of Cetuximab) to first response (PR or better). This endpoint is only applied for subjects with a confirmed BOR of PR or better.

**Progression free survival (PFS):** The PFS is defined as the time between the first dose date of Cetuximab to the date of disease progression or death, whichever is earlier. For patients without PD or death, those patients will be censored following the rules specified below.

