## 1.0 STUDY SYNOPSIS

Name of Sponsor:	Nektar Therapeutics
Name of Finished Products:	NKTR-255 Drug Product Erbitux®
Name of Active Ingredients:	NKTR-255 Drug Substance Cetuximab
Title of Study:	A Phase 1b/2, Open-label, Multicenter, Dose Escalation, and Dose Expansion Study of NKTR-255 Monotherapy or in Combination with Cetuximab as a Salvage Regimen for Solid Tumors
Duration of Treatment:	In Phase 1b, patients will receive an intravenous (IV) loading dose of cetuximab alone, followed 7 days later by the first combination treatment of IV cetuximab and IV NKTR-255 on Cycle 1 Day 1 (C1D1). Thereafter, IV NKTR-255 will be given in 21-day cycles in combination with weekly IV cetuximab.  In Phase 2, patients will receive either NKTR-255 in combination with cetuximab in 21-day cycles or will receive NKTR-255 monotherapy in 21-day cycles. Patients who achieve optimal response in the NKTR-255 in combination with cetuximab cohorts may move to NKTR-255 monotherapy maintenance given in 28-day cycles.  Patients will remain on treatment until meeting one of the criteria for discontinuation of treatment in Section 5.2.3.1.
Phase of Development:	Phase 1b/2
Objectives:	
The primary objectives are:
 
Phase 1b (Dose Escalation):
 
 
To evaluate the safety and tolerability, as well as define the maximum tolerated dose (MTD) and/or recommended Phase 2 dose (RP2D), of NKTR-255 in combination with cetuximab in relapsed or refractory (R/R) head and neck squamous cell carcinoma (HNSCC) or colorectal carcinoma (CRC)
 
 
Phase 2 (Dose Expansion):
 
 
To evaluate the safety and tolerability of NKTR-255 monotherapy and NKTR-255 in combination with cetuximab in R/R HNSCC, CRC. CCI [REDACTED]
 
To evaluate the efficacy of NKTR-255 in combination with cetuximab in R/R HNSCC or CRC by assessing the objective response rate (ORR) by Response Evaluation Criteria in Solid Tumors (RECIST) version 1.1
 
 
The secondary objectives are:
 
 
To evaluate the efficacy of NKTR-255 monotherapy in R/R [REDACTED] by assessing the ORR by RECIST 1.1
 
To evaluate the efficacy of NKTR-255 in combination with cetuximab and NKTR-255 monotherapy by assessing progression-free survival (PFS) and overall survival (OS)
 

CCI

CCI	

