### 6.3 Analysis Populations

**Enrolled Population:** All patients who receive at least 1 dose (or partial dose) of cetuximab or NKTR-255.

**Safety Population:** All patients who receive at least 1 dose (or partial dose) of NKTR-255.

**Cetuximab-only Population:** All patients who receive at least 1 dose (or partial dose) of cetuximab but without any dose of NKTR-255.

**DLT Population:** All patients who receive at least 1 dose of the combination treatment of NKTR-255 and cetuximab and who complete the DLT observation period or discontinue from

the study treatment due to a DLT will be included, where DLT window is 21 days since the first dose of NKTR-255.

**Response-evaluable Population:** The Response-evaluable Population is defined as patients who have measurable disease (per RECIST 1.1) at baseline, receive at least 1 dose (or partial dose) of NKTR-255, and have at least 1 post-baseline assessment of tumor response.

**Pharmacokinetic Population:** All patients in the Safety Population who receive at least 1 dose of treatment and have at least one evaluable PK concentration.

CCI

CCI

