## 6.6 Definitions

### Run-in period:

Eligible patients on combination therapy will receive cetuximab 400mg/m^2 IV as a loading dose during the study run-in period (Day -7). The run-in period therefore starts from the time the patient receives cetuximab and ends when the patient receives combination treatment of NKTR-255 +cetuximab.

**Study drug or study treatment:** Study drug or study treatment refers to NKTR-255 or cetuximab.

**Study day:** Study Day 1 (C1D1) is the first day that the combination treatment of NKTR-255 +cetuximab begins.

**Baseline:** Unless otherwise specified, the baseline value for each variable is the last non-missing value collected at the time (if collected) closest to, but prior to, the start of NKTR-255 administration. For triplicate ECG data, the record with three non-missing value will be considered as non-missing. If multiple measurements occur on the same day at the same time, or on the same day but the time is not available, the average of the measurements (for continuous data) will be considered the baseline value. When dosing times and/or observation times are not collected, it is assumed that protocol planned in-office assessments obtained on the day of the first dose of study drug are prior to administration of the first dose of study drug and therefore considered baseline values.

**Last known alive date:** The date of last known alive date will be derived for patients unknown to have died or known alive at the analysis cut-off by using following dates:

- Patient assessment dates (blood draws **CCI** [REDACTED], vital signs, performance status, ECG, tumor assessments, ECOG, or tumor biopsy dates)
- Start and end dates of anti-cancer therapies administered after study treatment discontinuation
- AE start or end date
- Concomitant medication start or end dates
- Last date of contact collected on the 'Survival follow-up' eCRF (do not use date of survival follow-up assessment unless status is 'alive')
- Study treatment start or end date
- Date of discontinuation for study participation on disposition eCRF pages (do not use if reason for discontinuation is lost to follow-up)

Only dates associated with actual examinations of the patient will be used in the derivation. Dates associated with a technical operation unrelated to patient status such as the date a blood sample was processed will not be used.

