**Table 3: PFS Censoring Rules**

Situation	Date of Disease Progression or Censoring	Outcome
No post-baseline tumor assessments and no death	first dose date of Cetuximab	Censored
No progression and no death, and no new anti-cancer therapy started	Date of last assessment showing no evidence of disease progression	Censored
New anti-cancer therapy started without progression before	Date of last assessment before the start of anti-cancer therapy showing no evidence of disease progression	Censored
Disease progression reported on one or multiple response assessments without new anti-cancer therapy before	Date of earliest evidence of PD	Progressed
Death without PD or new anti-cancer therapy before	Date of death	Death
Two or more consecutive missing tumor assessments, and no progression before the missing assessment	Date of the last assessment prior to the missing assessment showing no evidence of disease progression	Censored

**Overall Survival (OS):** OS is defined as the time from the first dose date of Cetuximab to death from any cause. Patients will be followed until their date of death, loss to follow-up, or withdrawal of consent for further follow-up for survival, regardless of the start of anti-cancer therapy. Patients who are lost to follow-up will be censored at their last date known to be alive. Patients who do not have date of death at data cut-off date will be censored at their last date known to be alive. Patients who do not have any follow-up since first dose date of Cetuximab will be censored on the first dose date of Cetuximab.

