## 7.5 Efficacy Analysis

Tumor response will be evaluated using RECIST 1.1 criteria ([Eisenhauer, 2009](#)). Tumor burden will be characterized prior to enrollment, and response assessments will be at approximately every 9 weeks starting from C1D1. A confirmed BOR of CR or PR requires the confirmation occurring at least 4 weeks after initial documentation. A BOR of SD requires a minimum of 63 days on study from C1D1 to the date of the first imaging assessment., Disease assessment at both scheduled and unscheduled visits will be used for efficacy endpoints. Disease assessments after new systemic anti-cancer therapy, surgical procedures or radiotherapy on target lesions will be excluded. Treatment beyond progression is allowed for qualified subjects. However, tumor assessment beyond progression will not be considered for response endpoints.

For efficacy endpoints including ORR, CBR, BOR summary will be based on the response-evaluable population. DOR and TTR will be summarized among confirmed responders. PFS, OS will be analyzed in the safety population. In addition, swimmer plot of tumor response and waterfall plot of best tumor size change will be generated based on safety population. Separate summary table and figures for efficacy analyses will be generated for HNSCC and CRC patients.

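### PFS and OS are timed from the Day -7 cetuximab dose but analysed only in patients who later received NKTR-255; separately, the TTR start date differs from the protocol

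*SAP*

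**What the plan says.** **Start of the clock.** SAP Section 6.6.1 states "The PFS is defined as the time between the first dose date of Cetuximab to the date of disease progression or death" and "OS is defined as the time from the first dose date of Cetuximab to death from any cause". In SAP Table 3, the PFS row "No post-baseline tumor assessments and no death" is censored at the first cetuximab date. In Phase 1b that date is the Day -7 loading dose, with NKTR-255 first given 7 days later at C1D1 (Protocol Section 1.0). SAP Section 6.6 describes the interval: "The run-in period therefore starts from the time the patient receives cetuximab and ends when the patient receives combination treatment of NKTR-255 +cetuximab".

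**Patients analysed.** SAP Section 7.5: "PFS, OS will be analyzed in the safety population". SAP Section 6.3 defines that set as "All patients who receive at least 1 dose (or partial dose) of NKTR-255". Patients who received cetuximab but never NKTR-255 form a separate Cetuximab-only Population. They belong to the Enrolled Population but not to the Safety Population. SAP Section 7.5 adds: "Separate summary table and figures for efficacy analyses will be generated for HNSCC and CRC patients".

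**TTR.** SAP Section 6.6.1 starts TTR at the first cetuximab dose. Protocol Section 9.6.3 summarises time to first response from C1D1.

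**The concern.** The clock starts about a week before a patient can qualify for the analysis. Nobody in the Safety Population can have died in that week, because a patient who dies before NKTR-255 never enters it. Either start date can be defended, and Protocol Section 9.1 leaves endpoint definitions to the SAP. The problem is the pairing of an early clock with a set defined by a later event.

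The SAP shows the mismatch itself. Its OS rule censors patients with no follow-up after first cetuximab at that dose, yet no Safety Population member can meet this condition, since each was dosed with NKTR-255 later. For adverse events, Section 7.6.2 does match clock and set: the NKTR-255 period goes with the Safety Population, and the any-drug period with the Enrolled Population.

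PFS and OS would be read as results in NKTR-255-treated patients while carrying time in which no death could count. A comparison with figures measured from another start date would be off by about a week. TTR as defined would not match the protocol's measure without an adjustment.

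**Working it through.** The documents state no expected PFS or OS, no event count and no number of run-in dropouts, so there is no figure to reproduce. All medians and dropout counts below are assumptions. Two effects have to be kept apart.

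**Inputs.** Run-in of 7 days, or 6 to 8 with the +1 day windows in Protocol Table 1. Month = 30.4375 days (SAP Section 6.5). Landmarks at 6, 9 and 12 months (SAP Sections 7.5.3 and 7.5.4). Scans every 9 weeks from C1D1, +7 days (Protocol Table 1). About 30 Phase 1b patients (Protocol Section 9.2).

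**(a) Start date: cetuximab clock versus C1D1 clock, same patients**

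- Offset: 7 / 30.4375 = 0.23 months. As a share of the median this is 0.23/2 = 11.5% at 2 months, 5.7% at 4, 3.8% at 6, 2.9% at 8 and 2.3% at 10.
- 6-month OS rate, exponential with λ = ln 2 / median. The excess is exp(-λ(6 - 0.23)) - exp(-λ × 6) = 1.44, 1.35, 1.20 and 1.06 points for medians of 4, 6, 8 and 10 months. A 6-day offset gives 0.91 to 1.23 points and an 8-day offset 1.21 to 1.65.
- PFS landmarks. The change depends on events between L × 30.4375 minus the offset and L × 30.4375 days after C1D1. With an 8-day offset these intervals are about 175–183, 266–274 and 357–365 days. The neighbouring scan windows are 126–133, 189–196, 252–259, 315–322 and 378–385 days. None overlaps, so scan-detected progression does not move these rates; only deaths without progression or off-schedule scans could.

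**(b) Pairing: Enrolled minus Safety, both on the cetuximab clock**

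Only this is the selection effect. With n treated patients, k run-in dropouts and complete follow-up:

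difference = k/(n + k) × (S_dropout - S_treated), with S_treated = 0.50.

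S_dropout is 0 for a run-in death. For a patient who leaves alive it is 0.25 with doubled hazard, 0.50 with equal hazard and 0.707 with halved hazard.

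| Points | Run-in death | Alive, hazard doubled | Alive, equal | Alive, hazard halved |
|---|---|---|---|---|
| n = 30, k = 1 | -1.6 | -0.8 | 0 | +0.7 |
| n = 30, k = 2 | -3.1 | -1.6 | 0 | +1.3 |
| n = 15, k = 1 | -3.1 | -1.6 | 0 | +1.3 |

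For example, n = 30 and k = 1 with a death: 1/31 × (0 - 0.50) = -1.6 points. The n = 15 row stands for one tumour type. A patient censored before the first death contributes 0. A simulation of 4,000 Kaplan-Meier analyses (n = 30, median 6 months) gave -1.61 for one death, -3.12 for two, -0.79 and +0.69 for one patient leaving alive with doubled or halved hazard, and 0.00 for one censored on day 3.

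Median OS on the same clock: solve S_treated(t) = 0.5 × (30 + k)/30. One run-in death lowers it by 4.5% to 4.6%, and two by 8.8% to 9.1%, for medians of 4 to 10 months.

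For PFS, a patient who leaves alive without a scan is censored at time zero under Table 3 and changes nothing.

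**Sampling error.** 1.96 × √(0.25/n) = 17.9 points with 30 patients and 25.3 with 15.

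**TTR.** A response at a scan 63 days after C1D1 is 63 + 1 = 64 days (2.10 months) on the protocol clock and 70 + 1 = 71 days (2.33 months) on the SAP clock, using the SAP's +1 convention.

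**The case against.** - **The Safety Population is an improvement.** Protocol Section 9.6.3 analyses PFS and OS in the Response-evaluable Population, which requires a post-baseline tumour assessment, and presents OS additionally in the Safety Population. Requiring a scan scheduled 9 weeks after C1D1 would leave out many early deaths. The SAP's choice cuts that conditioned interval to about a week, and SAP Section 12 discloses the change for PFS. This stands, and it is a reason to keep the population and move the clock.
- **The excluded patients are visible.** The Cetuximab-only Population is named, Section 7.1 counts each population, and Section 7.6.3 tabulates deaths in the Enrolled Population. This also stands, but those tables do not correct the Kaplan-Meier estimates.
- **Nothing is shown to occur.** With no run-in dropouts, effect (b) is zero. Entry requires a life expectancy above 12 weeks, so run-in deaths should be rare. Patients may also leave alive, for example after a severe cetuximab infusion reaction, although Protocol Section 5.7 sometimes lets NKTR-255 continue. Effect (a) is a choice of start date and is not in itself bias. All of this is right and keeps the point minor. The week in which no death can count is present whether or not anyone drops out.
- **A C1D1 start still leaves run-in deaths outside the curves.** True, but survival from first NKTR-255 among treated patients does not claim to include them. A from-cetuximab estimate does, and that one needs the Enrolled Population.
- **TTR.** The protocol defers detail to the SAP, and one bullet in SAP Section 12 is redacted. An unlogged change therefore cannot be shown, only that no readable entry covers it.

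**Conclusion.** The concern holds, as a minor point. The definitions alone establish that PFS and OS carry about 7 days in which no death can count. In the same patients this adds 0.23 months to each time and 1.1 to 1.4 points to the 6-month OS rate, under the exponential assumption; PFS landmark rates barely move.

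The selection effect has a fixed direction only for run-in deaths, which the present pairing omits and which would lower the estimates. Patients who leave alive could move OS either way. Its size depends on a dropout count the documents do not give, and for the cases examined it is well inside sampling error. The endpoints are descriptive and secondary, and dose selection does not use them. The TTR difference is real and is a separate matter of consistency with the protocol.

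**What to change.** In SAP Section 6.6.1 and Table 3, start PFS and OS at C1D1 (first NKTR-255 dose) for the Safety Population, including the dates used when a patient is censored at the origin. If a from-cetuximab version is wanted, present it in the Enrolled Population.

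Separately, start TTR at C1D1 as in Protocol Section 9.6.3, or record the change in SAP Section 12 if the redacted bullet does not already do so.

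The cost is SAP wording and one start-date variable, with no new data. Reported PFS and OS medians and TTR become about 7 days shorter. DOR, ORR, DLT and MTD results do not change.

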**Table 3: PFS Censoring Rules**

Situation	Date of Disease Progression or Censoring	Outcome
No post-baseline tumor assessments and no death	first dose date of Cetuximab	Censored
No progression and no death, and no new anti-cancer therapy started	Date of last assessment showing no evidence of disease progression	Censored
New anti-cancer therapy started without progression before	Date of last assessment before the start of anti-cancer therapy showing no evidence of disease progression	Censored
Disease progression reported on one or multiple response assessments without new anti-cancer therapy before	Date of earliest evidence of PD	Progressed
Death without PD or new anti-cancer therapy before	Date of death	Death
Two or more consecutive missing tumor assessments, and no progression before the missing assessment	Date of the last assessment prior to the missing assessment showing no evidence of disease progression	Censored

**Overall Survival (OS):** OS is defined as the time from the first dose date of Cetuximab to death from any cause. Patients will be followed until their date of death, loss to follow-up, or withdrawal of consent for further follow-up for survival, regardless of the start of anti-cancer therapy. Patients who are lost to follow-up will be censored at their last date known to be alive. Patients who do not have date of death at data cut-off date will be censored at their last date known to be alive. Patients who do not have any follow-up since first dose date of Cetuximab will be censored on the first dose date of Cetuximab.

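### The missed-scan row in the PFS censoring table sets no condition on what follows the gap, so it can discard clean later scans and leaves events directly after a gap unsettled

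*SAP*

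**What the plan says.** SAP Section 6.6.1 defines the endpoint: "The PFS is defined as the time between the first dose date of Cetuximab to the date of disease progression or death, whichever is earlier". The sentence leading into Table 3 adds: "For patients without PD or death, those patients will be censored following the rules specified below".

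Four of the six rows in Table 3 matter here. They are not numbered in the SAP; the numbers below count from the top.

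- **Row 2, no event:** "No progression and no death, and no new anti-cancer therapy started". Censored at the last scan without progression.
- **Row 4, progression:** "Disease progression reported on one or multiple response assessments without new anti-cancer therapy before". Event at the earliest evidence of progression.
- **Row 5, death:** "Death without PD or new anti-cancer therapy before". Event at death.
- **Row 6, missed scans:** "Two or more consecutive missing tumor assessments, and no progression before the missing assessment". Censored at "Date of the last assessment prior to the missing assessment showing no evidence of disease progression".

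Rows 2, 4 and 5 make no exception for missed scans, and the SAP states no order of precedence between rows.

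For DOR, Section 6.6.1 says: "Same censoring rules for PFS apply to DOR". The same paragraph, and Section 7.5.2, also censor responders who are alive and progression-free at their last evaluable scan before any later cancer therapy.

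**The concern.** A rule for missed scans is normally meant for an event whose timing is uncertain because it follows a long unobserved stretch. Row 6 does not say this. Its trigger looks only at the gap and at what came before it. This has two consequences.

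1. A patient who misses two scans, returns and is shown to be progression-free meets rows 2 and 6 together. Row 6 throws away progression-free time that was documented.
2. A patient who progresses or dies directly after the gap meets row 4 or 5 as well as row 6, so the table alone does not settle whether there is an event.

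Two programmers could follow the table and report different PFS times for the same patient. In an open-label study the choice would be made with outcomes visible. The situation is foreseeable: clinical deterioration can end treatment separately from RECIST progression (Protocol Section 5.7), and survival contact continues every 3 months after treatment ends (Section 5.2.7), so deaths can be recorded after scanning has lapsed.

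**Working it through.** No figure in the plan depends on this rule, so there is nothing to reproduce. The check applies each row literally to hypothetical patients.

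**Inputs**
- Scans every 9 weeks from C1D1 (Protocol Section 5.13.1).
- PFS starts at the first cetuximab dose (SAP Section 6.6.1), 7 days before C1D1 (Protocol Synopsis).
- Duration is later date minus earlier date plus 1; months are days / 30.4375 (SAP Section 6.5).

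**Formula:** an assessment or death at week w after C1D1 falls on PFS day 7w + 7 + 1.
- Week 9: 63 + 8 = day 71 (2.33 months)
- Week 30: 210 + 8 = day 218 (7.16 months)
- Week 36: 252 + 8 = day 260 (8.54 months)
- Week 45: 315 + 8 = day 323 (10.61 months)

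**Patients with a clean week 9 scan and weeks 18 and 27 missed**

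| What follows the gap | Other row that applies | Row 6 |
|---|---|---|
| Clean at weeks 36 and 45, alive | Row 2: censored day 323 | Censored day 71 |
| Progression at week 36 | Row 4: event day 260 | Censored day 71 |
| Death at week 30 | Row 5: event day 218 | Censored day 71 |
| Lost to follow-up | Row 2: censored day 71 | Censored day 71 |

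In the first line, 323 − 71 = 252 days of documented follow-up are lost. SAP Section 7.5.3 plans PFS rates at 6, 9 and 12 months. Under row 2 this patient is still at risk at 6 and 9 months; under row 6 the patient leaves at 2.33 months.

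Two further cases mark the limits. With one missed scan (week 18) and progression at week 27, only row 4 applies: 189 + 8 = day 197, no conflict. With no scans at all and death at week 20, row 5 gives an event on day 140 + 8 = 148, while row 6 has no post-baseline scan to date from.

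**Testing the lead-in sentence.** Suppose it confines row 6 to patients without progression or death. The second and third lines of the table are then settled by rows 4 and 5. Row 6 is left with the first line, where it discards clean follow-up, and the fourth, where it repeats row 2.

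**The case against.** The strongest reply is the lead-in sentence. It reserves censoring for patients without progression or death, and the PFS definition runs to whichever of those comes first. On that reading the event rows govern anyone with an event. A reader who looks only at the table might infer that row 6 flatly contradicts rows 4 and 5 with nothing to guide the choice. The documents do not support that: the lead-in points towards the event rows. The guidance is implied rather than stated, however. Row 3 censors at the start of new therapy even if the patient progresses later, so the lead-in is not a strict filter. It also does nothing for the patient with clean scans after the gap.

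Three other replies have weight. DOR has its own sentence for event-free responders, which favours the later date; but the paragraph also imports the PFS rules, so it conflicts with itself. Double gaps may be rare: scanning continues through dose delays (Protocol Sections 5.3.1.5 and 5.7) and after treatment stops without progression (Sections 5.2.3.1 and 8.2), and unscheduled scans count (SAP Section 6.1). Finally, censoring or counting an event directly after a gap is a convention, and neither choice is an error. All three limit the importance of the point. None supplies the missing condition.

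**Conclusion.** The point holds in this form. Row 6 is wrong as written for patients who resume clean scans, because it contradicts row 2 and the DOR text. For progression or death directly after a gap its scope is unclear, and on the reading that best avoids the clash it has no useful purpose.

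The size for one patient is large: 252 days of follow-up in the worked example, or an event at day 218 against censoring at day 71. The size for the study is limited. PFS is a secondary endpoint and is described by Kaplan-Meier, DOR is also descriptive, approximately 30 patients are planned, and the Phase 1b primary endpoints are DLTs and adverse events. No test or dose decision in the SAP uses PFS. A reader might infer that the reported PFS would be materially distorted. The documents cannot show that, because they give neither the frequency of double-missed scans nor the numbers at risk over time.

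The patient patterns are hypothetical, and visit windows are ignored.

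**What to change.** - Limit row 6 to progression or death that occurs directly after two or more consecutive missed scheduled assessments, with no evaluable assessment in between.
- State that patients whose scans resume without progression follow rows 2 to 5. The word directly matters: without it, progression found long after scanning has resumed would also be caught.
- State in rows 4, 5 and 6, and in the lead-in sentence, which row prevails for progression or death directly after a gap. Either convention is acceptable. Report the other as a sensitivity analysis. If the event rows prevail, row 6 serves only that sensitivity analysis.
- Wherever row 6 is applied, give a censoring date for a patient with no post-baseline scan before the gap.
- Apply the same wording to DOR, so that its own censoring sentence and the imported PFS rules agree.

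The cost is an edit to a few table rows and two sentences, plus one additional Kaplan-Meier run. No new data are needed.
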